With the global rise in Caesarean section, more and more women embark on pregnancy with previous Caesarean scar (3). It is estimated that one in every four term pregnancies requires IOL (4). With IOL in previous Caesarean section, the risk of uterine scar rupture with subsequent catastrophic maternal and neonatal outcomes is the greatest concern (5). Previous influential study (6) highlighted that IOL with prostaglandin conferred the greatest risk of uterine rupture (2.45%) in women with one previous Caesarean delivery. On the other hand, the risks of uterine rupture were lower and comparable among women whose labour induced without the use prostaglandin (0.77%) and women with spontaneous labour (0.52%). Among the various IOL methods, prostaglandin is more likely associated with shorter interval to achieve vaginal delivery and avoidance of oxytocin augmentation (7). Nevertheless, mechanical methods have lower risk of uterine hyperstimulation (7, 8) but have more risk of infection (7). As a result, obstetricians are facing dilemma on deciding the safe and effective method of IOL in women with previous Caesarean delivery.

In Sibug Hospital, membrane sweeping is routinely offered to women with previous Caesarean delivery who require IOL. This technique involves the examining finger passing through the cervix to rotate against the wall of the uterus, to separate the chorionic membrane from the decidua, or to massage around the cervix if the os is closed (1, 2). However, membrane sweeping may not exert its cervical ripening effect immediately and the delivery may be delayed by up to 8 days (9). This may render a proportion of women to resort to repeated Caesarean section for failed induction. The vaginal birth rates following membrane sweeping in women with unscarred uterus are ranging between 78%-90% (10-12). Among women with previous Caesarean delivery undergoing IOL with membrane sweeping, the reported vaginal birth rates were conflicting. A randomised controlled trial by Hamdan et al. showed vaginal

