- j. In Group 2, transcervical Foley catheter No. 18 F will be inserted under aseptic technique into the endocervical canal surpassed beyond the internal os. The balloon will be inflated with 60 ml of sterile water and the catheter is plastered to patient's thigh with gentle traction. The catheter will be checked for its position and the traction at 6 hours interval. If it were expelled spontaneously, it would not be re-inserted. Otherwise, the catheter will be removed after 24 hours.
- k. Post-induction CTG will be performed at 1 hour after the first membrane sweeping in Group 1 and after transcervical Foley catheter insertion in Group 2.
- l. The uterine contractions, maternal temperature and fetal heart rate (via handheld Doppler device) will be monitored every 4 hours.
- m. After 24 hours, improvement of modified Bishop score will be assessed.
 - i. If the cervix is favourable for amniotomy, amniotomy will be performed followed by augmentation with intravenous oxytocin.

- ii. If the cervix is still unfavourable and amniotomy is impossible, membrane sweeping will be continued for one more day in Group 1 whereas conservative management will be undertaken for one day in Group 2. Suitability for amniotomy will be reassessed on the next day.
 - n. After amniotomy, subsequent intrapartum management will be based on the hospital protocol.
 - o. Oxytocin augmentation will be started when desired contractions are not achieved at 2 hours after amniotomy or labour progress falls below the action line of partogram.
 - p. Our oxytocin infusion regime begins with 2 mU/min. An increment in dosage is made every 30 minutes until desired contractions of 3-4 in 10 minutes lasting 45-60 seconds. The maximum oxytocin dose is 16 mU/min.
 - q. Continuous CTG monitoring will be undertaken throughout the labour process.
 - r. Oxytocin augmentation will not be started or will be withheld when there is non-reassuring fetal heart rate.
 - s. If amniotomy is still impossible after 2 days of IOL, the ward Obstetrician will discuss with women regarding option of Caesarean section.
6. Criteria for suspending or terminating the study:

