 - a. Transcervical Foley catheter is found to have unreasonable and significant risks to subjects. The risks include uterine rupture, maternal sepsis, severe cervical trauma, and neonatal sepsis. However, all these serious adverse outcomes were infrequent risk based on literature review. Literature review showed that the risk of uterine rupture in Foley catheter arm is comparable to women with scarred uterus undergoing spontaneous labour (18, 25). There is small risk of maternal pyrexia or infection but no case of maternal or neonatal sepsis was reported (8, 28-30). Similarly, no case of cervical trauma was reported as well (31).
7. Study instruments:
 - a. Data collection form which consists of:
 - i. SECTION A: Subjects' demographic information (gravida, parity, gestational age, maternal height and weight, body mass index, details of previous Caesarean delivery, indication of IOL).

- ii. SECTION B: Subjects' induction outcomes (serial changes in modified Bishop score).
 - iii. SECTION C: Subjects' delivery outcomes (oxytocin requirement, mode of delivery, induction to delivery interval, overall duration of oxytocin augmentation, intrapartum details for the vaginal delivery (including instrumental delivery) subgroup, estimated blood loss, maternal and neonatal outcomes.
 - iv. SECTION D: 'Subjects' satisfaction on the care they received.
- b. Membrane sweeping:
- i. An IOL method involving the insertion of a digit past the internal cervical os followed by three circumferential passes of the digit causing separation of the membranes from the lower uterine segment.
 - ii. When the cervix is closed, a massage of the cervical surface for 15 to 30 seconds will be performed instead.
- c. Transcervical Foley catheter:
- i. An IOL method involving insertion of a balloon catheter under aseptic technique into the endocervical canal surpassed beyond the internal os.
 - ii. The balloon will be inflated with 60 ml of sterile water and the catheter is plastered to patient's thigh with gentle traction.
 - iii. Foley catheter is an indwelling catheter made of latex rubber.
- d. Modified Bishop score: (see Figure 1)
- i. A group of measurements made at internal examination, used to determine whether the cervix is favourable or not.
 - ii. The score is based on the station, dilation, effacement (or length), position and consistency of the cervix.
 - iii. A score of 8 or more generally indicates that the cervix is ripe (2).

Figure 1: modified Bishop score

Score	0	1	2	3

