 - i. Subjects may withdraw voluntarily from study at any time upon their request.
 - ii. Subjects are inappropriately enrolled without fulfilling inclusion/exclusion criteria.
 - iii. Subjects develop spontaneous labour before IOL procedure is undertaken.
- b. Follow up process:
 - i. The withdrawn subjects will be managed according to local protocol under Department O&G, Sibu Hospital.
 - ii. The withdrawn subjects data will be destroyed as it will not be used for data analysis.
- c. The withdrawn subjects will be replaced with new subjects in order to meet the required sample size.

TREATMENT AND PROCEDURES

1. Treatment and medications that are permitted during the trial:
 - a. Amniotomy
 - b. Oxytocin augmentation when contractions are not optimised
 - c. Abdominal and vaginal examination to assess labour progress
 - d. Intrapartum continuous fetal heart rate monitoring
 - e. Fetal scalp sampling in the presence of non-reassuring fetal heart rate
 - f. Instrumental delivery or emergency Caesarean section if indicated

2. Both IOL methods of membrane sweeping and transcervical Foley catheter do not contain drug or medication. Thus, the risk of uterine rupture is similar to spontaneous labour in women with previous Caesarean delivery. If scar dehiscence is highly suspected during labour, standard management with recourse to emergency Caesarean section will be undertaken.

3. Treatment and medications that are not permitted during the trial:
 - a. Vaginal prostaglandin E2

ASSESSMENT OF EFFICACY

1. Primary outcome:
 - a. Overall induction to delivery interval.
2. Secondary outcomes:
 - a. Induction outcomes:
 - i. Improvement of modified Bishop score at interval of 24 hours and 48 hours after induction.
 - ii. Whether oxytocin augmentation is required.
 - b. Delivery outcomes:
 - i. Mode of delivery.
 - ii. Duration of oxytocin augmentation overall and in vaginal delivery group.
 - iii. Induction to vaginal delivery interval.

- iv. Amniotomy to vaginal delivery interval.
- v. Vaginal delivery rate within 24 hours of induction and between 24-48 hours of induction.
- c. Maternal outcomes:
 - vi. Uterine hyperstimulation (> 5 contractions per 10 minutes for at least 20 minutes or a contraction lasting at least 2 minutes with/without abnormal fetal heart rate).
 - vii. Uterine rupture.
 - viii. Post-partum haemorrhage (estimated blood loss \geq 500 ml).
 - ix. Maternal pyrexia (temperature >38.0 °C once, or 37.5 °C on two occasions 2 hours apart).

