1. This study does not involve vulnerable subjects.

RESULTS (Dummy tables)**Table 1: Demographic characteristics**

Characteristics	Membrane sweeping	Transcervical Foley catheter	p-value
Age, years			
Parity			
Gestational age			
Ethnicity, n (%)			
Iban			
Melanau			
Bidayuh			
Malay			
Chinese			
Indian			
Others			
Foreigner			
Body mass index, kg/m ²			
Previous Caesarean section			
Tested scar			
Untested scar			
Indication of induction of labour			
Postdate			
Fetal growth restriction			
Hypertension			
Diabetes			
Others			

Table 2: Induction outcomes in two groups

Outcomes	Membrane sweeping	Transcervical Foley catheter	p-value
Bishop score at start of induction			
Bishop score after 24 hours of induction			
Bishop score after 48 hours of induction			
Change in Bishop score			
Oxytocin required			

Table 3: Delivery outcomes and maternal complications in two group

Outcomes	Membrane sweeping	Transcervical Foley catheter	p-value
Mode of delivery			
Vaginal			
Caesarean section			
Overall			
Induction to delivery interval			
Oxytocin augmentation duration			
Vaginal delivery			
Induction to delivery interval			
Amniotomy to delivery interval			
Oxytocin augmentation duration			

Within 24 hours of induction

Between 24-48 hours of induction

Indication for Caesarean section

Poor progress

Failed induction

Acute fetal distress

Suspected scar dehiscence

Others

Maternal complications

Uterine rupture

Uterine hyperstimulation

Post-partum haemorrhage

Maternal pyrexia

Duration of hospitalisation

Table 4: Neonatal outcomes in two groups

Outcomes	Membrane sweeping	Transcervical Foley catheter	p-value
APGAR score at 5 minutes			
Cord pH			
Birth weight			

[figure not shown]
REFERENCES

2. National Institute for Health and Clinical Excellence. *Inducing Labour*. NICE CG70. London: NICE; 2008.

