b) After 48 hours of induction

(only applicable to Foley group)

Achieved favourable Bishop (≥ 8) score: *(please tick)*

Yes

No

(if yes, proceed to sub-question;

if no, proceed to next question)

a) Interval to achieve favourable Bishop score

_____ (hours)

Achieved cervix allowing amniotomy: *(please tick)*

Yes

No

(if yes, proceed to sub-question;

if no, proceed to next section)

a) Bishop score at that time

b) Os dilatation at that time

_____ (cm)

c) Cervical length at that time

_____ (cm)

SECTION C: DELIVERY OUTCOMES

Oxytocin required during delivery (*please tick*) Yes No

Mode of delivery: (*please tick*)

- Vaginally Within 24 / 24-48 / > 48 hours of induction (*please circle*)
- Instrumentation Vacuum / forceps (*please circle*)
Indication: _____
- Caesarean section Indication: _____

Durations (regardless of final mode of delivery):

- a) Induction to delivery _____ (hours)
- b) Oxytocin augmentation _____ (minutes)

Durations (only for vaginal delivery including instrumental delivery):

- a) Induction to vaginal delivery _____ (hours)
- b) Amniotomy to vaginal delivery _____ (hours)
- c) Oxytocin augmentation _____ (minutes)

Estimated blood loss (EBL): ml

If EBL > 500ml, please mention cause: (*please tick*)

- a) Uterine atony
- b) Perineal trauma
- c) Retained placenta
- d) Coagulopathy
- e) Others *Please specify:*

Maternal complications: (*please tick*)

- a) Uterine rupture Yes No
- b) Uterine hyperstimulation Yes No
- c) Post-partum haemorrhage Yes No
- d) Maternal pyrexia Yes No

Neonatal outcomes:

- a) APGAR score at 5 minutes _____ To: NICU / SCN / mother (*please circle*)
- b) Cord pH _____
- c) Birth weight _____

SECTION D: MATERNAL SATISFACTION

If you had to repeat it all over again, would you take part in the study? (*please tick*)

Yes

No

If no, please provide reason(s). _____

Notes:

Uterine hyperstimulation : > 5 contractions per 10 minutes for at least 20 minutes or a contraction lasting at least 2 minutes with/without abnormal fetal heart rate

Post-partum haemorrhage : Estimated blood loss \geq 500 ml

Maternal pyrexia : Temperature >38.0 °C once, or 37.5 °C on two occasions 2 hours apart

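### Induction success is collected on the form but is not an outcome, and the listed Bishop-score comparison is made in women selected after randomisation

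*Combined protocol and SAP*

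**What the plan says.** The background gives the motivation: sweeping may act slowly, and "This may render a proportion of women to resort to repeated Caesarean section for failed induction". In Trial design, 5. Study procedure, the state of the cervix is the decision point. Item m assesses it at 24 h and sends women with a favourable cervix to amniotomy; the others wait or continue for another day. Item s then states "If amniotomy is still impossible after 2 days of IOL, the ward Obstetrician will discuss with women regarding option of Caesarean section".

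Assessment of efficacy, 2.a, lists two induction outcomes: "Improvement of modified Bishop score at interval of 24 hours and 48 hours after induction", and whether oxytocin is needed. Dummy Table 2 follows this with rows such as "Bishop score after 24 hours of induction", the change in score and oxytocin use.

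Appendix 3, Section B, collects more. It has yes/no items for "Achieved favourable Bishop" score (8 or more), with the "Interval to achieve favourable Bishop score", and for "Achieved cervix allowing amniotomy". The threshold comes from Trial design, 7. Study instruments, d: "A score of 8 or more generally indicates that the cervix is ripe".

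Failed induction is one row under the Caesarean indications in dummy Table 3, shown by arm in a table with a p-value column.

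**The concern.** Whether the cervix became ready is the step that each method is meant to achieve, and the one on which management turns at 24 h and 48 h. The plan collects a direct answer and then does not commit to analysing it.

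The outcome that it does list measures ripening on a scale that stops being available, or stops meaning ripening, once a woman has responded. Who is left to be scored depends on the treatment, so the groups compared are no longer the randomised ones. Because success is not pre-specified, either definition of it, or neither, could be reported after the results are seen.

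**Working it through.** The plan states no figure on this point, so the check is mainly of the text.

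**1. Where each form item reappears.** The two yes/no items and the hours to a favourable score were looked for in the specific objectives, the primary and secondary outcomes, Statistics 2 (t-test or Mann-Whitney), Statistics 3 (chi-square) and dummy Tables 1-4. None is there.

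**2. What the Table 3 row offers.** It can count only women delivered by Caesarean. Its source is a free-text indication on the form, written in an unblinded trial. It is not a listed outcome, Statistics 3 names no test for it, and no denominator is given.

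**3. Who has a Bishop score.**
- At 24 h: the plan lists vaginal delivery within 24 h as an outcome, so it expects some women to have delivered by then. They have no 24 h score, and the plan gives no rule for them.
- At 48 h: under item m.i, women favourable at 24 h have had amniotomy. If they are undelivered and still scored, the score describes labour and not ripening. Only women unfavourable at 24 h are still ripening.
- Direction: the arm with more responders by 24 h contributes fewer of them to the 48 h comparison. This follows from the procedure and needs no assumed rates.
- The form also takes a Bishop score if the catheter is expelled before 24 h. This exists in the Foley arm only, so it cannot fill the gap evenly.

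**4. Whether other listed outcomes replace it.** Oxytocin need is ambiguous: a woman whose cervix never allows amniotomy may receive none, and so may one who labours readily. Mode of delivery mixes failed induction with the other indications in Table 3 (poor progress, fetal distress, suspected dehiscence).

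**5. What a success comparison could show.** The documents give no failure rates, so these are assumed. With two-sided alpha 0.05 and power 0.8, n per arm = [1.96√(2p̄q̄) + 0.84√(p₁q₁ + p₂q₂)]² / (p₁ − p₂)².
- 30% v 10% failing: p̄ = 0.20, so (1.96√0.32 + 0.84√0.30)² / 0.04, which rounds up to 62 per arm. At 12 per arm, power is about 22%.
- 40% v 20% failing: p̄ = 0.30, so (1.96√0.42 + 0.84√0.40)² / 0.04, which rounds up to 82 per arm. At 12 per arm, power is about 18%.

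The 12 per arm is the plan's first stage; the final size is still to be calculated, for the primary outcome only. The measure is therefore supportive.

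**The case against.** The case against has several parts.

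- **A reader might infer that failed induction is never compared.** The documents do not support that: Table 3 shows it by arm with a p-value column. Mode of delivery, which carries the consequence named in the background, is a listed and tested outcome. Vaginal delivery within 24 h and at 24-48 h is also tested, and the primary interval from induction to delivery includes the early responders. What is missing is a defined comparison of ripening success.
- **A reader might infer that women in early labour go unscored at 24 h.** Nothing says so. The firm gap at 24 h is women already delivered. For women in labour the weaker point stands, that a score then does not measure ripening.
- **It is tempting to put a size on the bias.** Take an assumed true difference of 1.0 point (SD 2). If early labour in 1.6% v 4.7%, 4.7% v 11.1% or 11.1% v 21.6% of women removes their scores, the observed difference is 0.89, 0.81 or 0.75, an understatement of 11%, 19% or 25%. Every input is invented, and the model ties early labour to score improvement, so some attenuation is built in. It shows direction only.
- **The replacement has weaknesses.** Whether the cervix allows amniotomy has no stated threshold and is judged by unblinded staff. This stands, and is why the component with a cut-off should also be reported alone.
- **A form may collect more than is analysed, and the list of secondary outcomes is already long.** This is fair, and it limits the weight of the point. It does not rescue the 48 h score, which is a listed outcome and does not compare the randomised groups.

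**Conclusion.** The point holds in a limited form. Induction success is collected but is in no outcome, test or table. Failed induction is tabulated only as an undefined Caesarean indication. The listed Bishop comparison is conditional on events after randomisation, clearly so at 48 h and to a lesser degree at 24 h.

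The expected direction is against the faster-ripening arm. The documents do not allow a size to be given. The conclusion rests on the procedure in item m being followed and on the absence of any rule for women without a score. It does not touch the primary analysis. A yes/no measure with a fixed denominator answers the ripening question better and uses mostly data already collected, so the change should be made, though the trial does not depend on it.

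**What to change.** Add to Assessment of efficacy 2.a, to the chi-square list in Statistics 3 and to Table 2 a supportive secondary outcome:

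- **Definition:** successful ripening by 24 h and by 48 h, meaning Bishop score 8 or more, or cervix allowing amniotomy, or in labour, or delivered vaginally, by that time.
- **Not successful:** every other woman, including any Caesarean before success, whatever its indication.
- **Denominator:** all randomised women with retained data.
- **Estimate:** risk difference with 95% CI, with the Bishop 8 or more component also reported alone.

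Treat the 24 h and 48 h Bishop scores as descriptive, stating how many women were scored in each arm. Give the Table 3 failed-induction row the number randomised as its denominator.

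The costs are modest but real:

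- **Form:** it already holds hours to Bishop 8 or more and banded timing of vaginal delivery. It has no time beside the amniotomy item and no labour-onset item, so both must be added.
- **Multiplicity:** one more secondary comparison, at two time points.
- **Denominator:** Selection and withdrawal of subjects, 6, destroys the data of withdrawn women and replaces them, including those who labour before the procedure. Assessment of safety, 4.b, also withdraws women with a vasovagal attack after sweeping, which concerns one arm only. These rules must be reconciled with the denominator, and the number randomised but not retained should be shown by arm.

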- d. To compare the neonatal outcomes between membrane sweeping and transcervical Foley catheter for IOL in women with one previous Caesarean delivery.
 - i. APGAR score at 5 minutes.
 - ii. Cord pH.

- e. To compare women's evaluation on the care they receive between membrane sweeping and transcervical Foley catheter for IOL.

STATEMENT ON ETHICAL ISSUES

1. Institutional Review Board (IRB) Review:
 - a. The study protocol will be reviewed by Medical Research Ethics Committee (MREC) of Ministry of Health, Malaysia.
2. Patient information sheet and informed consent:
 - a. Written informed consent will be obtained from each subject prior to the enrollment.
 - b. Subjects will be told of the objective of this study in clear laymen's term. They will be informed of their rights as subjects and that their participation is voluntary.
 - c. Subjects will also be notified that if they choose to withdraw from the study at any time, they will be managed according to local protocol under Department O&G, Sibuh Hospital.
 - d. The information sheet specifies whom to contact if they are injured as a result of the study, and whom to contact with general information about the study.
 - e. The consent form specifies that the study staff, and governmental or regulatory authorities, have direct access to subject's medical record in order to make sure that the study is conducted correctly and the data are recorded correctly.
 - f. Compliance with informed consent will be monitored by the principal investigators.

TRIAL DESIGN

1. Study location:
 - a. This study will be conducted in the Department of Obstetrics and Gynaecology, Sibuh Hospital, Sarawak.

2. Study design:
 - a. A prospective randomised controlled trial (RCT) will be conducted.
 - b. The subjects will be followed-up from time of IOL till delivery.

3. Study endpoint:
 - a. The study endpoint is to confirm the superiority of membrane sweeping and transcervical Foley catheter for IOL in women with one previous Caesarean delivery.

4. Study duration:
 - a. This study will be conducted from 15 November 2017 till 24 September 2018.

5. Study procedure: (see flow chart in Appendix 1)
 - a. Approval will be obtained from the Medical Research & Ethics Committee, Ministry of Health Malaysia before conducting the study.
 - b. Pregnant women with one previous Caesarean section who are indicated for IOL and eligible will be recruited in the study.

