 - x. Duration of hospitalisation.
- d. Neonatal outcomes:
 - i. APGAR score at 5 minutes.
 - ii. Cord pH.

ASSESSMENT OF SAFETY

1. No adverse events (AEs) will be expected during the course of study because there is no involvement of pharmacological drug or product. Both methods of membrane sweeping and transcervical Foley catheter do not contain drug or medication. Thus, the risk of uterine rupture is similar to spontaneous labour in women with previous Caesarean delivery. However, maternal discomfort and vaginal bleeding following membrane sweeping and unknown latex allergy following transcervical Foley catheter insertion may occur, and subjects will be informed of this risk in the informed consent.
2. All other invasive (amniotomy, fetal scalp sampling in the presence of non-reassuring fetal heart rate, instrumental delivery or emergency Caesarean section if indicated) and non-invasive procedures (maternal vital signs observation and intrapartum continuous fetal heart rate monitoring) and evaluations (abdominal and vaginal examination to assess labour progress) included in this protocol are considered to be standard of care in evaluation and management of women with one previous Caesarean delivery undergoing IOL and would have been performed as part of routine practice.

3. Report of adverse events eg. SAEs, SUSARs.
 - a. When adverse event of any type occurs, local SAE/SUSAR report will be created by principal investigator and notified via SAE Platform on NMRR website.
 - b. Subjects who experience SAE/SUSAR will be followed up by principal investigator and a follow up report will be submitted.
 - c. For “Non-life threatening SUSARs” eg. latex allergy associated with Foley catheter insertion, vasovagal attack following membrane sweeping, and cervical tear, initial report is to be submitted within 15 calendar days followed by a follow up report.
 - d. For “Life threatening SUSARs” eg. uterine rupture and maternal sepsis, initial report is to be submitted within 7 calendar days followed by a follow up report within the next 8 calendar days.

4. Process and duration of follow-up of adverse events
 - a. Latex allergy associated with Foley catheter insertion
 - i. Foley catheter will be removed immediately.
 - ii. Steroids and anti-histamine will be administered as rescue medication.
 - iii. Closed monitoring of vital signs and oxygen saturation for 24 hours.
 - b. Vasovagal attack following membrane sweeping

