 - i. No further membrane sweeping will be performed.
 - ii. Affected subject will be withdrawn from the study.
 - iii. No rescue medication is needed as condition is self-limiting.
 - iv. Closed monitoring of vital signs and oxygen saturation for 24 hours.
 - c. Cervical tear
 - i. Examination under anaesthesia will be performed immediately.
 - ii. Cervical repair will be performed.
 - iii. Subject will be followed up till 42 days post-delivery (completion of puerperal period).
 - d. Uterine rupture
 - i. Emergency laparotomy will be performed immediately.
 - ii. Depend on the severity of uterine rupture, uterine repair or hysterectomy may be warranted.

- iii. Subject will be followed up till 42 days post-delivery (completion of puerperal period).
 - e. Maternal sepsis
 - i. Blood culture and high vaginal swab for culture will be taken.
 - ii. Broad spectrum antibiotics will be started as rescue medication.
 - iii. Unstable subjects will be nursed in intensive care unit.
 - iv. Subject will be followed up till 42 days post-delivery (completion of puerperal period).
5. Compensation of adverse events
- a. In the event of a bodily injury or illness directly resulting from the membrane sweeping or transcervical Foley catheter insertion, the department will pay for reasonable and necessary treatment.
 - b. The department is not responsible for medical expenses due to pre-existing medical conditions, any underlying diseases, any ongoing treatment process, subjects' negligence or willful misconduct, the negligence or willful misconduct of the investigators or the study site or any third parties.

STATISTICS

1. All results will be analysed using the Statistical Package for Social Sciences for Windows (SPSS for Windows).
2. Normality of numerical data (Bishop score, induction to delivery interval, induction to vaginal delivery interval, amniotomy to vaginal delivery interval, duration of oxytocin augmentation, duration of hospitalisation, APGAR score at 5 minutes, cord pH, neonatal birth weight) will be assessed using Kolmogorov-Smirnov analysis. Independent T-test (data with normal distribution) or Mann-Whitney U test (if data not normally distributed) will be used to compare these outcomes between the group of membrane sweeping and group of transcervical Foley catheter.
3. Chi-square test will be used to compare:

- a. The requirement of oxytocin augmentation following induction between the group of membrane sweeping and group of transcervical Foley catheter.

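### Objective 2.e (women's evaluation of their care) rests on one yes/no item about rejoining the study, an indirect proxy that no outcome list, test or table includes

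*Combined protocol and SAP*

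**What the plan says.** Objectives and Purpose, item 2.e, sets a comparative aim: "To compare women's evaluation on the care they receive between membrane sweeping and transcervical Foley catheter for IOL".

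Trial Design, item 7.a.iv (Study instruments), says that Section D of the data collection form records subjects' "satisfaction on the care they received".

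Section D itself (Appendix 3), headed Maternal Satisfaction, has one tick-box question, answered Yes or No: "If you had to repeat it all over again, would you take part in the study". A woman who ticks No is asked for her reasons in free text. A woman who ticks Yes is asked nothing more. The form does not say when the question is put.

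Assessment of Efficacy names the primary outcome as "Overall induction to delivery interval" and groups the secondary outcomes under induction, delivery, maternal and neonatal. The maternal group ends with "Duration of hospitalisation". No group contains a satisfaction or care-evaluation outcome.

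**The concern.** The objective and the instrument description both promise an evaluation of care, while the form asks about taking part in research. These are different things, and the plan offers no bridge between them.

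Two consequences follow. First, the answer cannot be read cleanly as a judgement on care or on the allocated method. Second, because the item is neither listed as an outcome nor given an analysis, what is done with it is left open. It could be dropped, or it could be reported under the form's own heading as maternal satisfaction, which it does not measure directly.

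Women's experience matters to this comparison. The background section cites discomfort as a frequent complaint after membrane sweeping, and Assessment of Safety, item 1, expects that it may occur. The form has no pain or discomfort item, so Section D is the only place where a woman's own view is recorded.

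**Working it through.** No arithmetic reproduces a figure here, because the plan gives no rate, effect size or power for this item. The check is to follow objective 2.e through the document and then ask what each possible answer would tell the analyst.

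**Step 1. Trace.**

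| Place | Is evaluation of care there? |
|---|---|
| Objectives and Purpose, 2.e | Yes, as a between-arm comparison |
| Trial Design, 7.a.iv | Yes, as Section D of the form |
| Appendix 3, Section D | One item, on rejoining the study |
| Assessment of Efficacy, items 1 and 2 | No |
| Statistics, item 2 (t-test or Mann-Whitney) | No; the list closes with "duration of oxytocin augmentation, duration of hospitalisation, APGAR score at 5 minutes, cord pH, neonatal birth weight" |
| Statistics, item 3 (chi-square) | No; it covers oxytocin requirement, mode of delivery, two vaginal delivery windows and four maternal complications |
| Dummy Tables 1 to 4 | No row |

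**Step 2. What the answer reveals.** Under Trial Design, items 5.e and 5.f, taking part means being allocated 1:1 by sealed envelope. A Yes therefore accepts a fresh allocation, which might be to the other method.

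| Woman's view of her care or method | Answer | What the form captures |
|---|---|---|
| Favourable | Yes | Yes, no reason |
| Unfavourable | Yes | Yes, no reason |
| Favourable | No (for example, does not want to be randomised) | No, with a reason if she gives one |
| Unfavourable | No | No, with a reason if she gives one |

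The first two rows are indistinguishable in the data. The last two can be separated only as far as the free text allows. So the information on care is one-sided: it comes only from women who decline.

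**Step 3. Size.** The comparisons listed under 2.a to 2.e number 2, 8, 5, 2 and 1, so 2 + 8 + 5 + 2 + 1 = 18. Objective 2.e is 1 of these 18. By lettered heading it is 1 of 5, but that count gives 2.e the same weight as 2.b with its eight comparisons.

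**Related point.** Selection and Withdrawal, item 6.b, destroys the data of withdrawn women, and Assessment of Safety, item 4.b, withdraws a woman who has a vasovagal attack after sweeping. Any Section D answer from such women would be lost too, whatever the item asks.

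**The case against.** The strongest reply is that the data do allow a comparison. The form records the allocated group and a yes/no answer, and Statistics, item 3, already has a rule for categorical data (chi-square, Yates correction, Fisher test). The proportion answering Yes can be computed and compared by arm. This stands. A reader might infer from the mismatch that objective 2.e is unanswerable; the documents do not support that. They support a weaker statement: the comparison available is of willingness to rejoin, and it is not pre-specified.

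A second reply is that the free-text reason deals with the woman who declines for something unrelated to her care, such as the consent process. This stands in part. The field exists and would often show the reason, but it does nothing for the woman who was unhappy with her care and ticks Yes.

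A third is that the objective concerns care, so a question only about the induction method would miss it as well. This is right, and the fix below puts care first and treats the method question as optional.

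A fourth is that the matter is minor: it is not the primary outcome, it does not drive the sample size and it is not a safety outcome. All of that is true and limits the size of the point. It does not remove the mismatch between a stated objective and the item collected for it.

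**Conclusion.** The point holds in a limited form. The plan states a comparison of women's evaluation of care, collects only an indirect proxy for it, and lists no outcome, test or table row for that proxy. Any comparison by arm would be unplanned and open to being mislabelled as satisfaction.

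The size is 1 of 18 listed comparisons, all other than the primary analysis being unaffected in the same way as the primary itself: induction to delivery interval does not depend on Section D. A reader might take the 1-in-5 count of lettered objectives to mean that a fifth of the trial's aims is lost; the count of comparisons does not bear that out. No bias or loss of power can be quantified, because the documents give no figures for this item.

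The conclusion assumes that no separate satisfaction questionnaire exists. Study instruments, item 7.a, names only Section D for this purpose. The Appendix 1 flow chart and the consent pages were not available in the text reviewed, and nothing here counts their content as missing.

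**What to change.** Replace or supplement the Section D item with a direct rating of satisfaction with the care received during induction, for example on a 0-10 scale. The range is a suggestion; the documents do not fix one. Optionally add a yes/no question on whether she would choose the same method again. Ask at one fixed time for every woman, such as before discharge.

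Then list the rating as a secondary outcome in Assessment of Efficacy. In Statistics, name Mann-Whitney for the rating and the existing chi-square/Fisher rule for any yes/no item. Add a row to the dummy tables.

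If the form can no longer be changed, reword objective 2.e to willingness to take part again, list that as the outcome, and do not report it as satisfaction with care.

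The cost is one form item, a line each in outcomes, statistics and tables, and no extra visit. It does need an amendment with ethics committee approval. The stated study period is 15 November 2017 to 24 September 2018; if recruitment has begun (an assumption), women already delivered will lack the new item, and the number answering it in each arm should be reported.
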